7.1.3. GSK3228836 Drug Induced Kidney Injury (Renal) Stopping Criteria

If any of the following are observed, results should be confirmed, and if confirmed, further evaluation for alternative causes should be pursued in consultation with the Medical Monitor:

- Persistent ACR ≥0.03 mg/mg (≥30 mg/g)
- Blood in urinalysis ≥5 red blood cells (RBC) per high power field (HPF) confirmed by urine microscopy
- Persistent elevation of serum creatinine (>26.52 μmol/L or 0.3 mg/dL change from baseline)

Following confirmation of the criteria above, further evaluation may include but not be limited to a 24-hour urine analysis, consultation with a nephrology specialist, renal ultrasound, urine microscopy, serum urea and creatinine, platelet count, urgent serum vasculitis screen (including ANCA, antinuclear antibody [ANA], double stranded deoxyribonucleic acid [dsDNA], cryoglobulins), serum protein electrophoresis (SPEP)/urine protein electrophoresis (UPEP), and complement panel (C3, C4, C5a, and Bb). Further evaluation and actions should be determined by the investigator in consultation with the Medical Monitor.

Treatment Hold/Treatment Discontinuation

- Hold study treatment in participants who develop ACR ≥0.5 mg/mg (500 mg/g), or eGFR >25% reduction from pre-dose range, pending consultation with the Medical Monitor and further evaluation of the cause.
 - If a dose is held, once eGFR increases to within baseline, ACR decreases to <0.5 mg/mg (500 mg/g), or the underlying cause of the decline in renal

function is corrected, weekly dosing may be reinitiated after consultation with the Medical Monitor

- Participants must be monitored weekly until ACR or eGFR resolve, stabilize, or return to within pre-dose range
- Hold study treatment in participants with ACR ≥ 2 mg/mg (2000 mg/g), perform further evaluation for acute glomerulonephritis, as clinically indicated. If acute glomerulonephritis is confirmed or probable (i.e., meets clinical definition of rapidly progressive glomerulonephritis [RPGN] if biopsy not feasible), GSK3228836 should be permanently discontinued
 - Participants must be monitored weekly until ACR resolves, stabilizes, or returns to within baseline values
- Delay in treatment of suspected RPGN should be avoided.

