7.1.4. GSK3228836-Induced Vascular Inflammation and Complement Stopping Criteria

If any of the following are observed, results should be confirmed with a repeat sample collection and analysis, and if confirmed, further evaluation for alternative causes should be pursued in consultation with the Medical Monitor.

Repeat sample collection of C3, C4, Bb, C5a would be triggered by changes in the clinical signs and symptoms of complement activation (≥ 2 + haematuria; increasing urine ACR; vasculitic or purpuric rash; peripheral neuropathy; jaundice). Additional complement analyses for example CH50, Factor B level, Factor H level, sC5b-9 should also be considered in discussion with the Medical Monitor and Safety Panels.

- **Persisting & deteriorating longitudinal trends in change from baseline for C3 and/or C4 defined as:**
 - If participant's baseline C3 and/or C4 is *within* the lab's normal range at baseline: there is a sequential decline in C3 and/or C4 once levels have fallen below LLN for ≥ 4 weeks OR
 - If participant's baseline C3 and/or C4 is *below* the lab's LLN at baseline: there is further sequential decline in C3 and/or C4 for ≥ 4 weeks OR
 - Regardless of baseline C3 and/or C4 level: there is a $\geq 80\%$ *reduction* in the participant's C3 and/or C4 level at any point AND
 - There is an associated ≥ 3 -fold *increase* in Bb and/or C5a from participant's baseline OR
 - There are associated biochemical sequelae for example, a rising high sensitivity C-reactive protein (hs-CRP); rising monocyte chemoattractant protein (MCP-1); new thrombocytopenia, new renal impairment with no other explanation such as intercurrent infection OR

- There are associated clinical sequelae, for example, ≥ 2 + haematuria; increasing urine ACR; vasculitic or purpuric rash; peripheral neuropathy; jaundice OR
- There is new cANCA or pANCA positivity
- **Persisting & deteriorating longitudinal trends in change from baseline for Bb and/or C5a where**
 - There is a ≥ 3 -fold increase in Bb and/or C5a over baseline AND
 - This is persisting or increasing week on week in sequential data plots OR
 - There are associated biochemical sequelae for example, a rising hs-CRP; rising MCP-1, new thrombocytopenia, new renal impairment with no other explanation such as intercurrent infection OR
 - There are associated clinical sequelae, for example, ≥ 2 + haematuria; increasing urine ACR, vasculitic or purpuric rash; peripheral neuropathy; jaundice or any combination of these OR

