 - There is new cANCA or pANCA positivity

Treatment Hold/Treatment Discontinuation

- Hold study treatment during evaluation of alternative causes for decreased C3 and/or C4 associated with increased inflammatory markers including one or more of hs-CRP, MCP-1, Bb and C5a
- Discontinue study treatment permanently if persistent change from baseline (≥ 4 weeks) in biomarker pattern (decreased C3/C4 associated with increased inflammatory markers including one or more of hs-CRP, MCP-1, Bb, C5a) without clear alternative explanation.
- Discontinue study treatment permanently if suspect clinical sequelae of complement activation, DIVI, vasculitis or autoimmunity regardless of biomarkers changes or persistence.

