Summary of post-baseline hepatobiliary laboratory abnormalities will be provided.

The worst-case urinalysis results post-baseline (on-treatment and off-treatment periods combined) relative to baseline will be summarized.

Summaries of result shifts from baseline, worst-case results post-baseline relative to baseline, and results with increase to \geq maximum toxicity grade post-baseline for chemistry, haematology, urinalysis, and immunology as applicable, will also be presented for treatment with GSK3228836 and PegIFN separately, by treatment arm and in total within each treatment period.

GSK3228836 liver chemistry monitoring and stopping event reporting will be summarized and listed. The liver monitoring and stopping criteria are described in the protocol Section 7.1.1.

GSK3228836 haematological monitoring and stopping events will be summarized and listed based on laboratory parameters (platelet count and anti-platelet antibodies). The haematological stopping criteria are described in the protocol Section 7.1.2.

GSK3228836 drug induced kidney injury (renal) monitoring and hold or stopping events will be identified programmatically and will be summarized and listed based on laboratory parameters (ACR, urinalysis red blood cells (RBC), serum creatinine, and eGFR). The kidney injury monitoring and stopping criteria are described in the protocol Section 7.1.3.

Drug induced vascular injury and complement monitoring/stopping event will be summarized and listed based on laboratory parameters (C3, C4, Bb, C5a, hs-CRP, MCP-1, p-ANCA, c-ANCA, eGFR, bilirubin, and platelet count). The drug induced vascular injury and complement monitoring and hold/stopping criteria are described in the protocol Section 7.1.4.

Hold/stopping event profile for GSK3228836 will be provided for any subject who has met hold or stopping criteria specified in protocol Section 7.1. Relevant information will be reported, including baseline characteristics, AEs/SAEs, concomitant medication, medical history/current medical conditions, study treatment administration details, laboratory values, and individual line plots of complement (C3/C4/C5a/Bb), inflammatory markers (hs-CRP/MCP-1), serum creatinine/creatinine clearance or eGFR/ACR, and platelet count.

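### The SAP's laboratory list for Protocol 7.1.4 events leaves out urine ACR and haematuria and cannot find the clinical permanent stop, so that event table can undercount

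*SAP*

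**What the plan says.** SAP 4.5.3.1 (Laboratory Data) gives the basis for the summary: "Drug induced vascular injury and complement monitoring/stopping event will be summarized and listed based on laboratory parameters". It then names 11 parameters, "C3, C4, Bb, C5a, hs-CRP, MCP-1, p-ANCA, c-ANCA, eGFR, bilirubin, and platelet count", and refers to Protocol 7.1.4 for the criteria.

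Protocol 7.1.4 uses clinical signs in three ways.

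- **Repeat sampling.** "Repeat sample collection of C3, C4, Bb, C5a would be triggered by changes in the clinical signs and symptoms of complement activation". The signs are haematuria of 2+ or more, followed by "increasing urine ACR; vasculitic or purpuric rash; peripheral neuropathy; jaundice".
- **Completing a monitoring trigger.** The same five signs appear as examples of clinical sequelae that can complete the C3/C4 trend criterion or the Bb/C5a criterion. They stand there as alternatives to biochemical sequelae or new ANCA positivity. The action for a trigger is that "results should be confirmed with a repeat sample collection and analysis", then evaluation with the Medical Monitor.
- **Permanent stop.** "Discontinue study treatment permanently if suspect clinical sequelae of complement activation, DIVI, vasculitis or autoimmunity regardless of biomarkers changes or persistence".

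Two further rules in 7.1.4 rest on biomarkers. One is a hold while other causes are evaluated for "decreased C3 and/or C4 associated with increased inflammatory markers including one or more of hs-CRP, MCP-1, Bb and C5a". The other is a permanent stop if that pattern persists for at least 4 weeks without a clear alternative explanation.

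**The concern.** The SAP sentence presents a table of 7.1.4 events but states only a laboratory basis. That basis already goes beyond complement and inflammatory markers. Bilirubin corresponds to jaundice, platelet count to new thrombocytopenia, and eGFR to new renal impairment. Urine ACR and haematuria are also laboratory measures and are named in the same criteria, yet they are absent. The stop for suspected clinical sequelae is defined as independent of biomarkers, so it lies outside any such list.

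At stake is the completeness of one safety table for a named adverse event of special interest. A participant stopped permanently for suspected vasculitis with normal complement would not be found from the 11 parameters. A reader would have to assemble the full picture from several outputs.

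**Working it through.** The plan gives no figure to reproduce. The check sets the SAP list against the protocol criteria.

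**Hold/stop rules in Protocol 7.1.4**

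| Rule | Needs | Covered by the SAP list? |
|---|---|---|
| Biomarker hold | C3, C4, hs-CRP, MCP-1, Bb, C5a | Yes, 6 of 6 |
| Biomarker permanent stop (4 weeks or more) | The same six | Yes, 6 of 6, apart from the judgement on alternative causes |
| Clinical permanent stop | Clinical suspicion | No |

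So 2 of 3 are covered.

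**Clinical signs named in Protocol 7.1.4**

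| Sign | SAP 7.1.4 list | SAP renal (7.1.3) list |
|---|---|---|
| Haematuria, 2+ or more | No | Urine RBC, under a different criterion |
| Increasing urine ACR | No | ACR, under different criteria |
| Vasculitic or purpuric rash | No | No |
| Peripheral neuropathy | No | No |
| Jaundice | Yes, through bilirubin | – |

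Four of five are absent from the 7.1.4 list (5 − 1 = 4), and two of those four are laboratory measures. Counting the renal summary, two of five are absent from both (rash and neuropathy). The renal criteria are not the same test: 7.1.3 uses "Blood in urinalysis ≥5 red blood cells (RBC) per high power field (HPF) confirmed by urine microscopy" and a persistent ACR of at least 30 mg/g, not 2+ haematuria or a rise in ACR alongside a complement change.

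**When a trigger is missed.** The completing elements are alternatives. A C3/C4 trend is missed only if there is no 3-fold rise in Bb or C5a, no listed biochemical sequela, no jaundice and no new ANCA positivity, and one of the four unlisted signs is the only completing element. A 3-fold rise in Bb or C5a is missed only if it also does not persist.

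**Are the data there?** Protocol Tables 2 and 3, GSK3228836 period:

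- Complement: 12 visits in Arm 1, 6 in Arm 2.
- Urine ACR: 13 and 7.
- Urinalysis: 24 and 12.

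Every complement day is also an ACR day and a urinalysis day in both arms.

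**Illustration of scale (hypothetical).** In an arm of 50, one missed participant is 1/50 = 2.0 percentage points. Exact (Clopper-Pearson) 95% upper limits:

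- 0/50: 1 − 0.025^(1/50) = 7.1%.
- 1/50: the p that solves (1 − p)^50 + 50p(1 − p)^49 = 0.025, which is 10.6%.

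**Why not count any ACR rise above baseline.** Assume that a participant's ACR values are exchangeable over time and that the confirming sample is the next scheduled one. The chance p that a later value exceeds baseline is then uniform on (0, 1). The probability of at least one run of two consecutive exceedances in n post-baseline samples is

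1 − [1/(n + 1)] × Σ C(n + 1 − k, k) / C(n, k), summed over k = 0, 1, ..., n/2 (n even).

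- n = 6 (Arm 2, 7 − 1): the sum is 1 + 1 + 10/15 + 4/20 = 2.867; 1 − 2.867/7 = 59.0%.
- n = 12 (Arm 1, 13 − 1): the sum is 1 + 1 + 55/66 + 120/220 + 126/495 + 56/792 + 7/924 = 3.712; 1 − 3.712/13 = 71.4%.

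Under these assumptions most participants would show a confirmed rise by chance.

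**The case against.** The sentence sits under Laboratory Data and does what that heading promises. The SAP treats haematology the same way: it lists only platelet count and anti-platelet antibodies, although Protocol 7.1.2 also holds dosing on signs or symptoms of thrombocytopenia. Clinical events belong with adverse events. The omitted signs are introduced as examples, are alternatives, and lead only to confirmation and evaluation, so leaving them out changes no hold or stop.

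Coverage elsewhere is also wide:

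- AESI outputs, including action taken if data permit (SAP 4.5.2.1), and AEs leading to permanent discontinuation (SAP 4.5.2).
- Reasons for stopping study intervention (SAP 6.1.1).
- Worst-case urinalysis, ACR increases to Grade 3 or higher, and out-of-range laboratory values (SAP 4.5.3.1).
- Hold/stopping profiles for anyone meeting a Protocol 7.1 criterion, with AEs and ACR plots (SAP 4.5.3.1).

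Most of this stands, and it is why the point is minor. What it does not answer is narrower. The list already includes laboratory counterparts of some sequelae, so leaving out ACR and haematuria does not follow from a biomarker-only intention. The profiles depend on knowing who met a criterion, and the SAP gives no rule for identifying those who met the clinical one. The AE tables show such cases by preferred term without tying them to 7.1.4.

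A reader might infer that vascular-inflammation stops go unreported, or that the biomarker rules are incompletely analysed. The documents support neither: the outputs above would show the stops, and both biomarker rules have all six markers.

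**Conclusion.** The mismatch is real and can be read directly from the two texts. Followed as written, the 7.1.4 event table can undercount monitoring triggers, when an omitted sign is the sole completing element, and clinical stops. The data are not lost and efficacy is unaffected.

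The number of participants affected cannot be derived. The shift from 7.1% to 10.6% only illustrates what one case does in an arm of 50. The count of four absent signs out of five should not be read as four-fifths of events missed: the signs are alternatives, and the repeat-sampling list does not itself define an event.

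The conclusion assumes that the stated laboratory basis is the whole derivation. The SAP speaks of programmatic identification only for renal events. The table layouts and the Output and Programming Specifications are not in the documents, and they could add a source. Severity: minor; a cheap improvement.

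**What to change.** Amend the vascular/complement sentence in SAP 4.5.3.1.

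1. Add urinalysis blood (2+ or more) and urine ACR to the parameter list, counted only together with the 7.1.4 change in C3/C4 or Bb/C5a. Set the threshold for an ACR increase with the clinical team. Any rise above the participant's own baseline is too unspecific.
2. Add one line, by arm, counting participants whose GSK3228836 was held or permanently stopped for a vascular-inflammation/complement AESI, taken from the AE action-taken field. Cross-reference it to the existing AESI and AE-discontinuation outputs.

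Matching AE terms for rash and neuropathy as completing sequelae is optional.

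The cost is a short SAP edit and minor programming on data already collected. Some participants will also be counted in the renal and AESI tables, which a footnote can state.

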4.5.3.2. Vital Signs

Summaries of grade increase in temperature, systolic blood pressure (SBP) and diastolic blood pressure (DBP) will be provided separately. These summaries will display the number and percentage of participants with any grade increase, increase to Grade 2, increase to Grade 3 and increase to Grade 4 (for temperature only), for worst case post-

baseline only. The grade definition for non-axillary temperature is: Grade 1 (38.0°C – <38.6°C), Grade 2 (38.6°C – <39.3°C), Grade 3 (39.3°C – <40.0°C), Grade 4 (\geq 40.0°C). The grade definition for SBP is: Grade 1 (140-159), Grade 2 (160-179), Grade 3 (\geq 180). The grade definition for DBP is: Grade 1 (90-99), Grade 2 (100-109), Grade 3 (\geq 110). The summaries will be produced for worst case post baseline only.

4.5.3.3. Electrocardiogram (ECG)

ECG data (absolute values and change from Baseline) will be summarised by visit and treatment arm only for the end of study analysis and won't be included in the interim analysis outputs.

4.6. Other Analyses

4.6.1. Subgroup Analyses

Descriptive summaries by subgroups defined in Table 7 will be provided. Number of responders, posterior mean and 95% equal-tail credible interval of the SVR response rate will be reported by subgroups as defined in the model specification section for each treatment arm. The corresponding posterior probability of SVR rate exceeding a range of clinically meaningful response rates will also be reported by subgroups as defined in the model specification section for each treatment arm. No statistical comparison between subgroups will be performed.

If the number of participants is too small (<5 per subgroup category) within a subgroup, then the subgroup categories may be redefined prior to unblinding the study. If the category cannot be refined further, then descriptive rather than statistical summaries may be presented for the specific subgroup.

Table 7 Subgroups and Subgroup Categories

Subgroup	Categories
HBeAg Status	Positive (\geq 0.09 U/mL); Negative (<0.09 U/mL)
Baseline HBsAg	Low (\leq 3 log ₁₀ IU/mL); High (>3log ₁₀ IU/mL) <=3, >3-3.5, >3.5-4 and >4
Age group	EMA: <18; \geq 18-64; \geq 65 – 84, \geq 85: FDA: \leq 18; \geq 19-64; \geq 65 Clinical and Epi (Group 1): <50; \geq 50
Sex	Male; Female
Race	American Indian or Alaska Native; Asian; Black or African American; Native Hawaiian or Other Pacific Islander; White
Baseline viral genotype	A; B; C; D; Other; Unknown
Baseline BMI	<30; \geq 30
Baseline ALT	\leq ULN; >ULN; \leq ULN, > ULN to \leq 2x ULN, > 2x ULN to \leq 3x ULN, > 3x ULN to \leq 5x ULN, > 5x ULN to \leq 10x ULN, >10x
Baseline METAVIR Fibrosis Score	If enough data are available (\geq 5 participants per group per arm): F0 – F2; F3
Time on current NUC	< 3 years; \geq 3 years
Type of current NUC	TAF/TDF; Entecavir; Other

Subgroup	Categories
Duration of Hep B Infection	<5 years; ≥ 5 years - <10 years; ≥ 10 years - <20 years; ≥ 20 years
Baseline mutations in the binding site	Present; Absent
Phase of HBV Infection (Strict Criteria)	
Phase 1; Phase 2; Other HBeAg-positive; Phase 3; Phase 4; Other HBeAg-negative, where phases are defined as below.
 
Phase 1 = HBeAg-positive, ALT ≤ ULN during screening and at baseline, HBV DNA > 10⁶ IU/ml during screening and at baseline Phase 2 = HBeAg-positive, ALT > ULN either during screening or at baseline, HBV DNA > 10⁴ IU/ml during screening and at baseline Other HBeAg-positive = HBeAg-positive, neither Phase 1 nor Phase 2 Phase 3 = HBeAg-negative, ALT ≤ ULN during screening and at baseline, HBV DNA < 20,000 IU/ml during screening and at baseline Phase 4 = HBeAg-negative, ALT > ULN either during screening or at baseline, HBV DNA > 2,000 IU/ml during screening and at baseline Other HBeAg-negative = HBeAg-negative, neither Phase 3 nor Phase 4

Phase of HBV Infection (Loose Criteria)	
Phase 1 loose; Phase 2 loose; Phase 3 loose; Phase 4 loose, where phases are defined as below.
 
Phase 1 loose= HBeAg-positive, ALT ≤ ULN during screening and at baseline Phase 2 loose = HBeAg-positive, ALT > ULN either during screening or at baseline Phase 3 loose = HBeAg-negative, ALT ≤ ULN during screening and at baseline Phase 4 loose = HBeAg-negative, ALT > ULN either during screening or at baseline

4.6.2. Subpopulations to Support Regulatory Consultation

To support consultation with regulators, key study population, efficacy, safety, and pharmacokinetic analysis will be repeated for the following subpopulations in the end of study analysis:

Japan subpopulation: All participants of Japanese heritage enrolled at sites in Japan.

China mainland subpopulation: All participants enrolled at sites in China Mainland.

East Asia subpopulation: All participants of a relevant Asian heritage (Asian – Japanese Heritage, Asian – East Asian Heritage or Asian – South East Asian Heritage) enrolled at sites in Japan, South Korea and China mainland.

4.7. Interim Analyses

Approximately every 3 months, an external IDMC will review results throughout the study to periodically evaluate safety data. Two interim analyses will be conducted for the study in addition to regular IDMC safety reviews.

There will be an initial unplanned, i.e. not pre-specified in the protocol, interim analysis of unblinded efficacy data to support internal decision making at a Development Review Board (DRB) meeting for the GSK3228836 platform trial (Study 218309) planned for 21-Apr-2022. Only a small sub-team of project-level team members will view these unblinded results and no changes to trial conduct or primary endpoint analyses will be made based on the results of this interim analysis. Further details describing this unplanned analysis will be provided in a separate analysis outline document.

Additionally, a series of administrative interim analyses (AIAs) not planned for in the protocol commenced September-2022 (see note to file: TMF-14859422 and Analysis Outline TMF-14917190) for the purpose of determining whether internal GSK resource should be allocated at-risk for future development of bepirovirsen followed by PegIFN sequential treatment. These future administrative interims will be provided on an ongoing basis (approximately monthly) to the GSK internal Data Review Committee (iDRC) for reference to support their formal decision-making. Below is a table with the monthly projections for the number of subjects with SVR data in each arm available at each AIA (and planned IA). Full details of the internal decision-marking framework are included in the iDRC charter.

Table 8 Projections for the Number of subjects with Primary Endpoint Available at planned IA (PIA) and each AIA

Note: September and October 2022 AIAs occurred prior to this iDRC being developed and approved. Details are included in the table below for awareness.

Review Month	Data Cut	AIA/ Planned IA	Total number of subjects	Projected number of subjects at Primary End point (OT WK 24)	
				Arm 1	Arm 2
Sep 22	22Aug22	AIA	28	1	27
Oct 22	03Oct22	AIA	58	13	45
Nov 22	11Oct22	PIA	66	18	48
Dec 22	28Nov22	AIA	88	35	53
Jan 23	09Jan23	AIA	100	47	53

There will also be a planned interim analysis as pre-specified in the protocol. The iDRC will have primary review responsibility of the pre-specified interim analysis results and determine if the data support an early Commit to Phase 3 (C2P3) recommendation to DRB. The pre-specified interim analysis will be triggered when all participants complete the end of treatment (EoT) visit (Week 48 for Arm 1 and Week 36 for Arm 2), and a sufficient number of participants have completed the 24-week off-treatment follow-up period (EoT+24wks) in order to assess the probability of C2P3. At this timepoint, it is expected that approximately 18 participants in Arm 1 and 48 participants in Arm 2 will be completers at the time of IA, i.e., participants who will have reached the end of the 24 week off-treatment follow-up period (EoT+24wks).

The primary objective of the pre-specified interim analysis is early assessment of program-level futility and success. Full details of the internal decision-marking framework for the planned IA are included in the iDRC charter.

